3.0 PARTICIPANT NUMBER, RECRUITMENT, COHORT CHARACTERISTICS AND ELIGIBILITY

3.1. Participant Number

We anticipate recruitment and enrollment of approximately 465 patients for this study and assume a 10% overall attrition rate after enrollment. We will recruit from among patients who consent to the COH IRB 07047 Precision Medicine protocol and who have been or had been diagnosed with cancer. For 07047 overall, we estimate approximately 4000 total patients in year 1 of Precision Medicine (beginning CY 2021), 6000 total patients in year 2, and larger numbers yet in subsequent years, demonstrating likely feasibility. Given that patients who consent to 07047 may receive WES (e.g. GEM ExTra), Panel

Testing (e.g. HopeSeq), and/or germline (e.g. Invitae) as part of their care, they will have the genomic testing that is necessary for this education intervention study.

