4.1.2 Patient Follow Up Survey

The follow up surveys will either be mailed to the participant, along with a return envelope, provided electronically and/or by text message via REDCap survey link, or completed via phone or Zoom call with a staff member, according to patient preference. For patients who opt to complete their follow-up surveys via phone or Zoom call, study staff will not assist them in selecting the correct answers for questions pertaining to their understanding of cancer and genetics. Study staff will follow-up with patients once a week within 2–3-week window to encourage completion of the survey. We will attempt to contact non-responders up to five times to encourage survey participation.

Understanding of personal genomic knowledge will be assessed through an adapted version of a measure created by Freedman and colleagues¹, which evaluated women's knowledge of their personal cancer ER and HER2 status using a two-item question (3 response options; yes/no/I don't know). Our adapted questions will evaluate patients' recall of genomic testing results and the implications of their results (i.e., harmful and unknown). Patient recall will be assessed at all survey timepoints (i.e., at baseline, 10 days, 3 months and 9-months following results disclosure with a clinician).

Engagement in care will be assessed by a novel item that queries patients as to whether WES prompted questions to care providers (yes, no, don't know). We will use items adapted for our CSERII study to ask patients if they recall changes to their cancer treatment as a result of their genomic test results. We will also assess engagement via interactive functionality of HOPE-Genomics (see below). Seeking and sharing information about genetic tests will be assessed using two items from the Health Information National Trends Survey (HINTS) 4 that were adapted for our CSERII study.⁷

Satisfaction with physician/patient communication around the results of gene testing will be assessed with a 7-item measure adapted from HINTS 3 & 4. Satisfaction with care will be assessed using a single item measure from Charles and colleagues that was created to evaluate satisfaction with genetic counseling and that was adapted for our CSER1 study.¹⁴ We have also included two novel questions to assess whether patients (1) recalled asking their healthcare providers about their genetic test results and (2) recalled receiving a copy of their genetic test report.

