6.0 DATA ANALYSIS

As noted in Section 4.0, we are administering the survey items in order to help with item reduction for the trial. We will generate descriptive statistics (e.g., distributions, means) in order to evaluate for ceiling and floor effects. An amended survey will be submitted prior to administration.

Primary outcome (i.e., patient knowledge, recall rates) will be assessed at the 10-day post-disclosure timepoint.

We will be using MRA and survey data to evaluate if participants received contextual guideline-concordant care. This will involve review of receipt of prophylactic surgery, chemoprevention, targeted therapy for germline mutations, consultation with genetic counseling/ genetic specialists, informing family members, and family member cascade testing. To generate concordance scores for patients already on active therapy, patients will be asked about their current and/or planned cancer treatment at baseline and at each follow-up timepoint in the study (i.e., chemotherapy, radiation therapy, cancer-directed surgery, hormone therapy, immunotherapy, and targeted therapy). Patients will be considered as being contextually guideline-concordant if they receive at least 75% of the recommended guidelines. In sensitivity analyses, we will vary the cutoff for guideline- concordance between 50% and 100%. Survey data will also be used to evaluate usability of the HOPE-Genomics application, the psychosocial impact of using the tool, engagement in care, genetic knowledge, and understanding of genomic test results

6.1 Sample Size and Accrual Rate:

We plan to anchor our cohort on patients with somatic testing. We expect to accrue 465 patients: 155 per each arm. We assume that there will be a 10% attrition rate among accrued patients, leaving us with a final analytical sample of 390 patients. For the first 3 months, we assume that 17 patients are enrolled each month, during which time we will evaluate and optimize study processes. After this we will increase monthly accrual to 35 patients. We expect to be complete with accrual in 16 months. Patient participation will be approximately 7 months consisting of baseline pre-testing followed by genetic testing/results disclosure and then post-testing. The estimated total study time including analysis will be 26 months.

6.2 Statistical Analysis Plan:

The study data will consist of three main areas:

- 1) patient knowledge testing and clinical care recommendations via survey-based questions

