6.2.1 Primary Outcome

In Aim 1, recall rates of personal genomic results at the 10-day post-disclosure timepoint for Arms 2 and 3 of the study will be pooled together so that the main comparison is a two-sample test of proportions between patients under usual care (Arm 1) vs. patients with any exposure to the HOPE-Genomics tool (Arms 2/3). Pilot studies indicate that a recall rate for patients with an actionable somatic finding are approximately 39% under usual care. An analytical sample of 390, assuming a 39% recall rate under usual care (Arm 1: n = 130) with a 15% improvement using the tool (Arms 2/3: n = 260), will be sufficient to detect a difference in proportions with 80% power and alpha = 0.05 (two-sided with no adjustment for multiplicity). Rates of recall will be analyzed using a two group Chi-Square test of equal proportions, and logistic regression when controlling for covariates such as age and education level. The overall fit of the model will be examined using Hosmer-Lemeshow goodness-of-fit test and ROC curves. If any normality issues arise, non-parametric techniques such as the Mann-Whitney test will be deployed. Recall rates will be defined as the number of participants who correctly recall somatic test results, which will be assessed in the second question of the 10-day post-disclosure survey.

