Test-related distress: We hypothesize that patients who view HOPE-Genomics will have lower test-related distress than patients in the usual care group: Patients will be assessed at 3 post-disclosure time points (T1-T3) using the PAGIS Certainty Scale and the FACToR. Some patients may have little test-related distress, whereas others may score higher (e.g., if testing reveals cancer or non-cancer related disease risk). Test-related distress is thought to decrease with time from the disclosure visit. We will summarize test-related distress at each time point, as well as change score. We will examine baseline characteristics to evaluate the potential for bias. In addition to complete case analysis, sensitivity analyses (e.g., using weighted methods) may occur to evaluate bias. We will use clustered Wilcoxon test for mean score comparison between groups at each time point. In addition, mean change in score from T1 to T3 will be modeled using GEE model adjusting for patient characteristics. We will use Autoregressive (AR1) and compound symmetry working correlation matrix to account for repeated measurement correlation and within-physician correlation. The significance of the coefficient will be tested to determine difference between two groups.

General genomic knowledge: We hypothesize that patients in the Return of Results plus Pre-test Education (Arm 3) arm will have better general genomic knowledge than the Return of Results only and Usual Care arms (Arms 1/2). To examine this, we will compare the pre/post test scores between the intervention group (Arm 3) and the control groups (Arms 1/2). The pre/post test scores will be calculated by taking the difference in score between pre/post tests and then comparing the mean differences with an independent T-test between control groups (Arms 1/2) versus the exclusive exposure to the HOPE-Genomics tool educational content (Arm 3). We also hypothesize that Arm 3 will have better knowledge of the difference between germline and somatic testing, as measured in the modified Lung-MAP instrument, which has been adapted and implemented in our survey. We will test this difference as above, testing the mean difference in scores of the modified Lung-MAP instrument across Arms 1 and 2 vs Arm 3.

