8.7 Participant Withdrawal from Research

At any time after signing the informed consent document, participants may elect to withdraw from participation in this protocol as follows: A participant may (1) withdraw from future study activities but permit clinical data collection to continue, (2) withdraw from future study activities and disallow the collection of clinical data, (3) remain amenable to study activities but disallow retention of PHI data, or (4) elect to withdraw completely from the study whereby all data will no longer be made available for research. Participant withdrawal, including the nature of withdrawal, will be documented in the Master List which will be kept in a password-protected file, accessible only by authorized study staff using secure COH computers. The request to withdraw from studies will also be documented in the patient's medical record via Epic. If they do not wish to participate but are interested in exploring other options such as talking with their care team or a social worker, we will provide appropriate referrals.

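### Primary 10-day recall has no stated denominator or missing-answer rule, and loss to the survey could differ between Arm 1 and Arms 2/3

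*Combined protocol and SAP*

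**What the plan says.** - **Endpoint.** Section 6.2.1: "Recall rates will be defined as the number of participants who correctly recall somatic test results". This is a count taken from one 10-day survey item. No denominator is given, and no score for a missing answer.
- **Analysed number.** Section 6.1: "We expect to accrue 465 patients: 155 per each arm", then "We assume that there will be a 10% attrition rate among accrued patients, leaving us with a final analytical sample of 390 patients". Section 6.2.1 sizes the test on that number, "assuming a 39% recall rate under usual care (Arm 1: n = 130" against 260 in the pooled tool arms. It describes the pooled group in terms of exposure to the tool.
- **Analysis principle.** Intention-to-treat is stated in Section 6.2.2 for guideline-concordant care (Aim 2). It is not stated for Aim 1.
- **Missing data.** The only text is in Section 6.2.3, for exploratory test-related distress, and it is optional: "In addition to complete case analysis, sensitivity analyses (e.g., using weighted methods) may occur to evaluate bias".
- **Ways to have no answer.** Section 4.1.2: "We will attempt to contact non-responders up to five times to encourage survey participation". Section 8.7 lets a participant stop study activities, or "elect to withdraw completely from the study whereby all data will no longer be made available for research".
- **Who gets the survey.** Section 4.5.1 sends it to every enrolled patient about ten days after EHR release. Appendix H (Arms 2/3) says a survey will follow once the tool has been viewed. Appendix K, the Arms 2/3 survey letter, thanks the patient for having viewed it. Appendix M ends participation for a patient without tool access and says their information will be removed.

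**The concern.** Patients are randomised right after enrolment (Section 4.1), but the primary outcome exists only for those who answer a later survey. If the test is run on responders, it compares the arms as randomised only if loss is unrelated to recall or acts alike in both groups. The Arms 2/3 scripts give a documented reason why it might not: as worded, they make the survey or continued participation depend on a step that Arm 1 does not have, since Arm 1 gets the tool only after its last survey. If less engaged patients were lost more often from Arms 2/3, observed recall there would rise without any tool effect. With no rule in the plan, the choice of denominator and scoring would also stay open until the data are in hand.

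**Working it through.** **1. The plan's own power.** Inputs from Section 6.2.1: 39% vs 54%, n = 130 and 260, two-sided 0.05.

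- Pooled rate = (130 × 0.39 + 260 × 0.54)/390 = 0.49.
- Null SE = √[0.49 × 0.51 × (1/130 + 1/260)] = 0.0537.
- Alternative SE = √[0.39 × 0.61/130 + 0.54 × 0.46/260] = 0.0528.
- Power = Φ[(0.15 − 1.96 × 0.0537)/0.0528] = 80.2%. The stated 80% reproduces.
- An observed 39% vs 54% gives z = 0.15/0.0537 = 2.79, p = 0.005.

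**2. Who is outside the 390.** 465 − 390 = 75, and 75/465 = 16.1%. The stated 10% would leave 465 × 0.9 = 418.5. That mismatch is a separate arithmetic error. By group, 155 − 130 = 25 and 310 − 260 = 50, so the planned numbers assume equal loss of 16.1%.

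**3. How far missing answers could move the estimate.** Expected correct answers are 0.39 × 130 = 50.7 and 0.54 × 260 = 140.4. The observed difference is +15.0 points.

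- All 25 missing in Arm 1 correct, all 50 in Arms 2/3 wrong: 140.4/310 − 75.7/155 = −3.5 points.
- The reverse: 190.4/310 − 50.7/155 = +28.7 points.

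These are limits, not forecasts.

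**4. Type I error if loss differs by arm (assumed inputs).** True recall is 39% in every arm. Loss is 10% in Arm 1 and 19% in Arms 2/3, so n = 139.5 and 251.1, about 390 in total. Arms 2/3 non-responders recall at r, so Arms 2/3 responders show (0.39 − 0.19r)/0.81.

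- r = 20%: 0.352/0.81 = 43.5%.
- Arm 1 loss random: Arm 1 shows 39.0%, a bias of +4.5 points.
- Arm 1 non-responders also recall at 20%: Arm 1 shows (0.39 − 0.10 × 0.20)/0.90 = 41.1%, a bias of +2.3 points.

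| Recall among non-responders, r | Type I error, Arm 1 loss random | Type I error, same r in every arm |
|---|---|---|
| 10% | 25% | 10% |
| 20% | 14% | 7% |
| 30% | 7% | 5.5% |

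If loss and r are both equal across arms, responder recall is equal and the error stays at 5%.

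**5. Scoring non-response as not recalled, at the planned effect (155 vs 310).**

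- Assumed 10%/19% loss: 0.39 × 0.90 = 35.1% vs 0.54 × 0.81 = 43.7%; z = 1.79, p = 0.07.
- Equal 16.1% loss: 0.39 × 390/465 = 32.7% vs 0.54 × 390/465 = 45.3%; z = 2.60, p = 0.009.

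**The case against.** The strongest reply is that the documents give no loss rate by arm. The only split that follows from them is equal, and under equal loss with the same non-responder recall the responders-only test keeps its 5% level. Even the harsh scoring in step 5 then leaves p = 0.009. Arm 1 receives the same survey with the same contact attempts, so less engaged patients can ignore it there too. Allowing for that cuts the illustrated error from 14% to 7%. Section 4.4 gives Arms 2/3 extra reminders and access help, which could raise their response. It also releases results in the tool 3–14 days after the EHR, so the 10-day survey can fall due before the tool is viewed. All of this stands: neither the direction nor the size of any differential loss is known.

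It also stands that the loss figure is not a survey response rate. Section 3.1 says "assume a 10% overall attrition rate after enrollment", without tying it to the 10-day survey. Section 3.4.1 admits germline-only patients, so part of the gap between 465 and 390 could be patients with no somatic result to recall.

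What does not stand is that sending the survey to everyone settles the matter. Five contacts may reduce non-response but do not score those who never answer, and Section 4.5.1 conflicts with Appendices H, K and M.

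**Conclusion.** The point holds as an unfilled gap in the primary analysis. There is no denominator, no missing-answer rule and no as-randomised statement for Aim 1; the sample size implies responders only; and scripts used in Arms 2/3 alone could make loss differ by arm. Exclusion of non-responders is implied by the 390, not written as a rule.

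The size of any bias is hypothetical. Under the assumed 10%/19% loss and 20% recall among Arms 2/3 non-responders, type I error is about 14% or about 7%, depending on who is lost from Arm 1. Under equal loss and equal non-responder recall it is 5%. Whether the conclusion depends on scoring (p = 0.07 or 0.009) rests on the same assumed split.

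A reader might infer three stronger things that the documents do not support:

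- That 10–16% of patients will give no 10-day answer. The 10% is overall attrition, and the 16.1% comes from the mismatch with 390.
- That non-response is tied to not using the tool, and only in Arms 2/3. The scripts make this possible but do not establish it.
- That failed sequencing, mentioned in Appendix O, is a further route to a missing answer. That is general patient education, and a patient without a somatic result raises a question of who belongs in the endpoint population.

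The change should be made because it bears on the primary conclusion and costs little, not because inflation has been shown.

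**What to change.** In Section 6.2.1, define the primary comparison by assigned arm regardless of tool use, with all randomised patients who have a released somatic result as the denominator.

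Reconcile Section 4.5.1 with Appendices H, K and M, so that the 10-day survey is sent, and collected data are kept, regardless of tool use. The exception is a participant who withdraws all data under Section 8.7.

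Beside the responders-only chi-square test, pre-specify:

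- (a) multiple imputation or response weighting by arm, using baseline and pre-test knowledge, education, health literacy and 3-month recall;
- (b) non-response scored as not recalled;
- (c) a tipping-point analysis that varies recall among non-responders separately by arm.

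Analysis (a) assumes that missingness is explained by the measured variables, so (c) is the one that directly tests loss linked to recall itself. Patients whose data are removed cannot be imputed. Report them, and 10-day response, by arm.

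The cost is SAP and script wording plus modest programming, with no extra patients or data collection. The downside is that the supporting estimates may be less favourable than the responders-only result. Correct the 10%/390 mismatch separately.

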6.2.1 Primary Outcome

In Aim 1, recall rates of personal genomic results at the 10-day post-disclosure timepoint for Arms 2 and 3 of the study will be pooled together so that the main comparison is a two-sample test of proportions between patients under usual care (Arm 1) vs. patients with any exposure to the HOPE-Genomics tool (Arms 2/3). Pilot studies indicate that a recall rate for patients with an actionable somatic finding are approximately 39% under usual care. An analytical sample of 390, assuming a 39% recall rate under usual care (Arm 1: n = 130) with a 15% improvement using the tool (Arms 2/3: n = 260), will be sufficient to detect a difference in proportions with 80% power and alpha = 0.05 (two-sided with no adjustment for multiplicity). Rates of recall will be analyzed using a two group Chi-Square test of equal proportions, and logistic regression when controlling for covariates such as age and education level. The overall fit of the model will be examined using Hosmer-Lemeshow goodness-of-fit test and ROC curves. If any normality issues arise, non-parametric techniques such as the Mann-Whitney test will be deployed. Recall rates will be defined as the number of participants who correctly recall somatic test results, which will be assessed in the second question of the 10-day post-disclosure survey.

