We will test if the use of HOPE-Genomics will result in higher rates of uptake of evidence-based genetically guided care (e.g., patient receipt of guideline concordant care, cascade testing) than usual care: Our primary goal will be to assess whether or not the uptake of contextual guideline-concordant care differs between the two arms. The primary objective is to test the null hypothesis of no intervention effect on the outcome. We expect that patients in the intervention arm will have higher rate of uptake of contextual guideline-guided care than patients in the control arm. A two-sided Type I error of 0.05 will be used for all statistical tests. We will consider two-sided p-value less than 0.05 as a statistically significant. Patients will be considered concordant ($Y=1$) if they undergo a predetermined percentage of genetically guided care and discordant ($Y=0$) otherwise. Using an intention-to-treat analysis, the proportion of concordant patients will be modeled using the logistic regression approach for binary outcome (PROC LOGISTIC in SAS [Cary, N.C.]). We will use compound symmetry and unstructured working correlation matrix to account for correlation between patients within the same physician. The odds ratio of the concordant patients between the intervention and control arms will be calculated using the group coefficient in the Logistic model. The significance of the coefficient will be tested to determine treatment group difference. In addition, we will use Kauermann and Carroll (KC) correction for robust SEs if the number of physicians is small.¹¹ To evaluate the success of randomization, we will test the differences in characteristics of physicians and patients between the two arms. The Logistic model will include statistically significant characteristics as covariates. Logistic will also be used to model the percentage of the rate of uptake of the genetically guided care per patient, treated as a binomial variable, and include the within-physician correlation, to test for treatment group difference.

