Appendix M: Patient Script Inviting Remote Tool Viewing w/ Test Results

Hello, my name is [YOUR NAME] and I am a clinical research assistant at City of Hope is there a [([name]) PATIENT NAME] here?

Hi Mr/Ms. [PATIENT NAME]. I am reaching out to you because you recently agreed to participate in our HOPE-Genomics study, in which patients are receiving and reviewing their genetic test results through our HOPE-Genomics App or website. Does this sound familiar?

[IF NO] That's okay, I can provide you with a quick summary.

For this study you were approached by me or another clinical research assistant either in clinic or via phone to be consented in a study, that your physician or genetic counselor may have mentioned to you in your appointment. For this study we are testing our HOPE-Genomics app or website with patients to help patients review their genetic test results. After this initial consent, you may have completed a survey about cancer and genetics at the clinic or chosen to complete it at home on paper or through a survey link. Does this sound familiar?

[IF STILL NO] thank them and end the call.

[IF YES] Great. First, thank you very much for participating in our study. I am contacting you because the next phase of your participation in the study is to review your genetic tests results via our tool. Did you receive your login information via email?

[IF NO] That's okay, I can provide you with that information now.

[PROVIDE LOGIN INFORMATION]

[IF YES]

Have you had an opportunity to view the tool?

[IF NO]

Are you having any trouble accessing the tool?

[IF YES]

We would be happy to assist you troubleshoot this issue now. Do you have a few minutes to do so now?

[IF NO]

I would be happy to schedule an appointment to discuss this in the next few days. Unfortunately, we have had some recent procedural changes at our institution due to COVID-19, which limit our ability to meet with patients in person. As such, we are primarily meeting with patients via web conference (i.e. Zoom) or phone. Would you like to schedule a time to meet with one of our study staff?

Protocol 02/17/2023

HOPE-Genomics Clinical Trial

Protocol Packet: 13

[IF YES]

Great! Thank you so much for accommodating us. [SCHEDULE TIME]

[IF NO] Thank them for the participation thus far and let them know that unfortunately we cannot continue with the study unless they have access to the tool. Rest assured that all the information you provided for this study will be removed.

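### The recall comparison is worded by tool exposure with no intention-to-treat rule, and the patient scripts can remove non-viewers from Arms 2/3 only

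*Combined protocol and SAP*

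**What the plan says.** - **Primary comparison (Section 6.2.1).** Recall rates "for Arms 2 and 3 of the study will be pooled together", and the contrast is "patients under usual care (Arm 1) vs. patients with any exposure to the HOPE-Genomics tool (Arms 2/3". No analysis population is named, and nothing is said about a patient in Arm 2 or 3 who never opens the tool. Section 6.2.3 uses the same wording for 3-month recall.
- **Sample size (Section 6.2.1).** Power of 80% is claimed "assuming a 39% recall rate under usual care (Arm 1: n = 130") and "with a 15% improvement using the tool (Arms 2/3: n = 260"). The only allowance, in Section 6.1, is 10% attrition.
- **Intention-to-treat.** It appears once, for guideline-concordant care in Section 6.2.2: "Using an intention-to-treat analysis, the proportion of concordant patients will be modeled".
- **Non-use is foreseen.** Section 4.4 has patients log in on their own time, with access tracked and reminders sent. Appendix M has staff ask "Have you had an opportunity to view the tool".
- **Who is surveyed.** Section 4.5.1 asks all enrolled patients for a survey about 10 days after results are released in the EHR. Appendix H tells intervention patients that the follow-up survey comes once they have viewed the tool. Appendix K, the survey invitation for those arms, opens by thanking them for having viewed their results in it.
- **Who stays in.** In Appendix M, a patient who has not viewed the tool and declines a help session is told that the study cannot go on without tool access and that the information already given will be removed.

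**The concern.** A randomised comparison is protected only if both sides keep everyone assigned to them. Arm 1 has no tool to open during follow-up, so no Arm 1 patient can be lost for failing to open it. If non-viewers in Arms 2/3 are not surveyed, or their data are deleted, the less engaged patients leave one side only. Engagement plausibly goes with recalling a test result, so a recall difference could appear with no tool effect.

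This can happen even if the analyst groups patients by randomised arm, because the selection takes place when the data are collected. An intention-to-treat label alone would not repair it.

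A second question follows for power. If non-users are kept, as they should be, the average gain over Arms 2/3 may be smaller than the gain in users. The plan does not say which of the two its 15 points represents.

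**Working it through.** **1. The plan's own power.** Inputs from Section 6.2.1: p1 = 0.39, p2 = 0.39 + 0.15 = 0.54, n1 = 130, n2 = 260, two-sided alpha 0.05.

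- Pooled rate = (130 × 0.39 + 260 × 0.54)/390 = 0.49
- SE under the null = √[0.49 × 0.51 × (1/130 + 1/260)] = 0.0537
- SE under the alternative = √[0.39 × 0.61/130 + 0.54 × 0.46/260] = 0.0528
- Power = Φ[(0.15 − 1.96 × 0.0537)/0.0528] = Φ(0.85) = 80.2%

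The stated 80% reproduces, with the 15% read as percentage points. Read as a relative gain (39% to 44.85%), power would be 19%.

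**2. The passages side by side.**

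| Question | Reading by arm | Reading by exposure |
|---|---|---|
| Who is compared? | 6.2.1: Arms 2 and 3 pooled, n = 260 | 6.2.1 and 6.2.3: any exposure to the tool |
| Who gets the 10-day survey? | 4.5.1: all enrolled patients | Appendix H: those who have viewed the tool |
| Are non-viewers' data kept? | 8.7: withdrawal and removal are the participant's choice | Appendix M: staff announce that participation ends and data are removed |

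The right-hand entries in the last two rows have no Arm 1 counterpart. Appendix L invites usual-care patients to the survey with no such condition.

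**3. Illustration of the bias with no tool effect.** The documents give no uptake rate, so these are assumptions. A share u of Arms 2/3 never opens the tool and is lost. Those patients would recall g less often than openers, tool or no tool. Recall over the whole arm is 0.39, and the 10-day survey is otherwise complete. Then:

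- Recall in openers = 0.39 + u × g, so the false gain is u × g
- Patients left in Arms 2/3 = 260 × (1 − u)
- Rejection probability = Φ[(ug − 1.96 SE0)/SE1] + Φ[(−ug − 1.96 SE0)/SE1], with the SEs formed as in step 1

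| u | n left | g = 10 points: false gain, type I error | g = 20 points: false gain, type I error |
|---|---|---|---|
| 10% | 234 | 1 point, 5.4% | 2 points, 6.5% |
| 20% | 208 | 2 points, 6.5% | 4 points, 11.1% |
| 30% | 182 | 3 points, 8.2% | 6 points, 18.3% |

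For the last cell: openers at 0.45, pooled rate 0.425, SE0 = 0.0568, SE1 = 0.0565, and Φ[(0.06 − 0.1113)/0.0565] = 18.2%, plus 0.1% in the other tail.

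**4. Power if the 15 points is the effect in users.** Assume also that non-users gain nothing. By randomised arm, p2 = 0.39 + 0.15 × (1 − u). The last column uses 465 × 0.9 = 418.5 analysed patients, split 1:2, because 10% attrition from 465 leaves about 418 and not 390.

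| Non-use u | p2 | Power, 130 vs 260 | Power, about 418 analysed |
|---|---|---|---|
| 0% | 0.540 | 80.2% | 82.9% |
| 10% | 0.525 | 71.4% | 74.4% |
| 20% | 0.510 | 61.1% | 64.2% |
| 30% | 0.495 | 50.1% | 52.9% |

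**The case against.** The best defence is that Section 6.2.1 already means analysis by arm. It pools Arms 2 and 3, attaches the arm labels to the exposure phrase, and counts 260 patients, twice Arm 1, with nothing deducted for non-users. Any exposure can simply mean either tool arm, with or without pre-test education. The general-knowledge analysis in Section 6.2.3 likewise uses exposure as a label for Arm 3. Nothing in Section 6 says non-openers are dropped. This stands: a reader might infer that the plan prescribes an as-treated analysis, and the text does not support that. It does not answer Appendices H and M, which act before any analysis begins.

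Two other inferences are tempting and should be resisted.

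- **That the plan defines its groups in several conflicting ways.** Section 6.2.2 asks whether "uptake of contextual guideline-concordant care differs between the two arms" in a three-arm trial, and Section 6.2.3 hypothesises that "patients who view HOPE-Genomics will have lower test-related distress than patients in the usual care group". The first is loose wording for intervention against control, within an analysis labelled intention-to-treat. The second is a hypothesis sentence, and the analysis after it compares groups. Neither defines an analysis set by exposure.
- **That the stated power is wrong.** The arithmetic is right. If the 15 points is already the average over everyone in Arms 2/3, the 80% stands.

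It is also fair that every size in steps 3 and 4 rests on assumed uptake, and that non-openers and 10-day non-responders may overlap, so non-use may not simply add to attrition.

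**Conclusion.** The concern holds as an unresolved conflict that bears on the primary result. The wording of the comparison is ambiguous, no intention-to-treat rule covers Aim 1, and two patient scripts, followed as written, remove less engaged patients from Arms 2/3 only. That would bias the recall comparison towards the tool.

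The size cannot be fixed from the documents. Under the assumptions in step 3 the bias runs from negligible (1 point, 5.4% type I error) to serious (6 points, 18%). The upper end needs both 30% non-use and a 20-point recall gap.

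The power point is conditional. It applies only if the 15 points is an effect in users, and the power figures below 80% also assume no gain in non-users. The larger sample implied by 10% attrition softens the loss but does not restore 80% at 10% non-use.

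**What to change.** 1. **Analysis rule.** In Sections 6.2.1 and 6.2.3, state that recall is analysed by randomised arm, Arms 2/3 pooled against Arm 1, whether or not the tool was opened.
2. **Survey and data retention.** Reconcile Appendices H and M with Section 4.5.1. The 10-day survey should go out on the same schedule in every arm regardless of viewing, and data from non-users should be kept unless the patient withdraws them. Limiting the denominator to 10-day responders would not be enough while the scripts stand, because response would itself depend on viewing.
3. **Sensitivity analysis.** Add one that counts 10-day non-responders as not recalling, in every arm.
4. **Meaning of the 15 points.** State whether it is the average over all Arm 2/3 patients or the effect in users. If the latter, restate power for the uptake the sponsor expects. The figures in step 4 show the scale and should not be written into the plan as expected values.

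The cost is changes to plan and script wording, one extra analysis, and possibly a less favourable stated power. One consequence should be accepted openly: Section 4.4 puts results in the tool about 3-14 days after the EHR, so with a common 10-day schedule some patients may answer before they have seen their results there.
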